	
results will be provided to the DSMB. Primary analysis of the data will be conducted after all randomized participants have completed 24 weeks Cohorts B and C may be analyzed separately. Unblinded data summaries including safety outcomes and exploratory efficacy assessments will be prepared for the sponsor during the study using all data collected through Weeks 24 and 36.

Pharmacokinetic considerations	N/A
Statistical Analyses	
Analysis Populations
 
Safety The safety population will consist of all subjects who receive one or more doses of TOL-3021 or placebo and have any follow-up safety data.
 
Efficacy The efficacy population is by intention-to-treat: all subjects randomized to treatment and taking at least one dose of medication will be included in the ITT population. Appropriate imputation methods may be used for missing data.
 
Statistical Methods
 
Primary Efficacy Analysis
 
The analysis of the primary outcome, change from baseline in log-transformed MMTT-stimulated 4-hour mean C-peptide AUC at multiple time points will test the null hypothesis of “no treatment group difference” versus the two-sided alternative using the intent-to-treat (ITT) cohort. The primary hypothesis test will be the treatment group estimate from a repeated measures mixed model fit to a log-transformed 4-hour C-peptide AUC response at 12, 16 and 24 weeks, adjusted for the baseline C-peptide AUC, age group and duration group.

Estimated Trial Initiation Date	10 June 2019
Estimated 52-Week Trial Completion Date	30 Sep 2021
Estimated Follow-up Period Completion Date	30 Sep 2023

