## **3 TRIAL DESIGN**

The SUNRISE study is a prospective, multi-center, randomized, placebo-controlled trial in subjects aged 12.0 to <41.0 years diagnosed with T1D, as defined by ADA criteria, and within 5 years of diagnosis. Time of diagnosis is defined as the first day of insulin administration. The study is triple-blind through the analysis at Week 24, after which the Sponsor will be group unblinded. The study will continue through Week 52 as double-blind with site staff and subjects blinded. Subjects will be stratified by duration (zero up to 1 year and 1 year up to five years) to ensure balance of disease duration across treatment and placebo groups in each strata. For analytical purposes, all subjects 12-<41 will be considered cohort A, subjects aged 12-<18 will be considered cohort B and subjects aged 18-<41 will be considered cohort C. For subjects aged 12-<18 (Cohort B), dosing will be staggered with an initial 6 subjects aged 14-<18 being enrolled with the last subject having a minimum of 2 injections with at least 1 week follow-up after the 2nd injection. Safety data from this cohort will be evaluated before opening the study subjects 12 and older. Subjects should be randomized no sooner than 6 weeks after diagnosis, unless blood glucose is adequately controlled as indicated by time in range >55% with CGM. Screening assessments will include a physical examination, a fundus photography examination, chemistry and hematology safety labs, urinalysis, urinary protein screen (if positive a 24-hour collection for urine protein and creatinine will be obtained), HbA1c, presence of T1D antibodies, and a MMTT. Up to 99 qualified subjects who meet all selection criteria will be randomized in a 2:1 ratio to treatment with TOL-3021 or placebo and treated for 52 weeks (Figure 3). Subjects will agree to diabetes management during the

study with the goal of maintaining HbA1c levels of approximately 7.0% without frequent episodes of hypoglycemia.

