## 13 STATISTICAL CONSIDERATIONS

### 13.1 Sample Size/Power Considerations

Up to 99 subjects will be randomized 2:1 to active and placebo treatments. For analytic purposes all subjects 12- <41 years of age will be considered cohort A. A minimum of 18 and a maximum of 24 subjects aged 12 and <18 years of age will comprise Cohort B. Adult subjects aged 18- <41 will comprise cohort C. The proposed study is powered to detect approximately an overall 13% difference between treatment and placebo groups in a repeated measures mixed model analysis of the mean plasma C-peptide AUC over 4-hour MMTT at Week 12, 16, and 24 weeks as compared to the subject's baseline. A total of 90 subjects will provide 90% power to detect this difference at a significance level (alpha) of 0.05; a total of up to 99 subjects will be randomized to allow for an anticipated drop-out rate of approximately 10%. Insulin secretion as reflected by C-peptide declines more rapidly in younger patients, including adolescents. TOL-3021 is expected to have equal or even greater effect in the adolescent population compared to the effect observed in the phase 2a study of adult subjects only. An effect was detectable in the 17 adults who received 12 weeks of 1.0 mg treatment in that study. Based on assumption of an overall difference between treatment and placebo groups of 20%, then a minimum of 18 adolescents aged 12- <18 (Approximately 12 active and 6 placebo) would provide 80% power to detect a difference at a significance level (alpha) of 0.05, providing an initial estimate of efficacy and a description of safety in this population Cohort B (ages 12- <18) and cohort C (ages 18- <41) and will be analyzed separately as well as combined.

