### 13.2 Interim Data Analysis

When the first 30 treated subjects have completed the Week 12 visit, summary and individual safety data will be submitted to the DSMB for review to support expanding enrollment in TOL-3021 studies to adolescent subjects aged 12.0 to <18 years of age.

An interim analysis will be performed when the first 30 subjects complete 24 weeks of treatment. The DSMB will review data in a blinded manner. Alpha spending will be utilized by the O'Brien-Fleming method, with 0.0052 of the alpha being spent at the interim analysis, saving the remaining 0.0498 alpha for the final analysis. Criteria for the review and any decision will be agreed with the DSMB. A small group of Tolerion management who are not related to the conduct of the trial will be provided unblinded data results from this interim analysis for administrative purposes. This list of individuals to be unblinded will be identified, and the process for these individuals to receive unblinded data results will be finalized prior to the unblinding for this interim.

Unblinded data summaries including safety outcomes and efficacy assessments will be prepared for the sponsor during the study using all data collected through Week 36. A final analysis of the data will be conducted at 52 weeks.

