### **13.3.3 Efficacy Analysis**

The analysis of the primary outcome, MMTT-stimulated 4-hour mean C-peptide AUC at multiple time points will test the null hypothesis of “no treatment group difference” versus the two-sided alternative using the intent-to-treat (ITT) cohorts. The treatment-group main effect hypothesis test will be derived from a repeated measures mixed model of the log-transformed 4-hour C-peptide AUC response at 12, 16 and 24 weeks, adjusted for the baseline C-peptide AUC, age group and T1D-duration group. Missing data for this analysis will be imputed for each subject based on any available data. To be imputed, a data point must have data for the visit before and the visit after the missing data point, and the slope between the two non-missing visits will be used to impute the missing data. A secondary method using a mixed model for repeated measures (MMRM) approach will also be utilized for the primary and secondary endpoints that cannot be imputed using the approach above. Additional details for this approach will be provided in the statistical analysis plan.

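### The protocol contradicts itself on which population carries the primary test, and it attaches a full 0.05 level to the adolescent cohort that its alpha plan does not cover

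*Protocol*

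**What the plan says.** Section 3 (Trial Design) defines three overlapping groups. It states that "For analytical purposes, all subjects 12-<41 will be considered cohort A"; those aged 12 to under 18 are Cohort B, and those aged 18 to under 41 are Cohort C. A is therefore the union of B and C.

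Some places point to more than one test:

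- Section 13.1 says that B and C "will be analyzed separately as well as combined".
- Section 13.1 gives two power statements at the same level. For the whole trial: "A total of 90 subjects will provide 90% power to detect this difference at a significance level (alpha) of 0.05". For a minimum of 18 adolescents and a 20% difference, the sample "would provide 80% power to detect a difference at a significance level (alpha) of 0.05".
- Section 13.3.3 tests the primary null "versus the two-sided alternative using the intent-to-treat (ITT) cohorts", in the plural.

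Other places point to one test:

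- The synopsis version of the primary analysis "will test the null hypothesis of “no treatment group difference” versus the two-sided alternative using the intent-to-treat (ITT) cohort", in the singular.
- The synopsis, under Data Handling and Blinding, says "Cohorts B and C may be analyzed separately". Section 3 also makes this optional.
- The primary model, in both the synopsis and Section 13.3.3, adjusts for age group.
- Section 13.1 describes the Cohort B result as a first estimate of efficacy.
- Section 13.2 has a single alpha plan: 0.0052 at the interim, "saving the remaining 0.0498 alpha for the final analysis". It allots nothing by cohort.

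**The concern.** The protocol fixes a significance level for Cohort B and makes separate analyses mandatory in one place and optional in others. It does not state which analysis decides the trial.

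This matters because a stand-alone adolescent result is foreseeable. Section 13.1 expects an effect in adolescents at least as large as in adults, and the cohort may hold as few as about 12 active and 6 placebo subjects. If the combined analysis were null and Cohort B or C significant, the text in 13.1 and 13.3.3 could be cited for calling the primary aim met, while the synopsis could be cited against it. The sponsor is to be group-unblinded after the Week 24 analysis, so the question should be settled before then.

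**Working it through.** **1. The alpha plan as stated.** Section 13.2 gives 0.0052 and 0.0498. Their sum is 0.0550, so they do not divide 0.05. With correlation √t between looks, where t is the information fraction at the interim, the two-look type I error is 1 − P(|Z1| < 2.794, |Z2| < 1.962):

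- t = 30/90: 0.0528
- t = 30/99: 0.0530

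So the plan for A alone already runs at about 5.3%.

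**2. Inputs for the cohort question.**

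- Total N: 90 (evaluable) to 99 (randomised), Section 13.1.
- Cohort B: 18 to 24 subjects, Section 13.1.
- Levels: 0.05 two-sided for A and for B, Section 13.1. No level is stated for C; 0.05 is assumed where C is counted.
- Assumed: no treatment effect, equal variance and the same 2:1 ratio in B and C, and one final look.

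**3. Formula.** Let f = n_B/N. With Z_B and Z_C independent standard normal,

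Z_A = √f · Z_B + √(1−f) · Z_C, so corr(Z_A, Z_B) = √f.

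- A and B: P = 1 − P(|Z_A| < 1.96, |Z_B| < 1.96)
- A, B and C: P = 1 − P(all three |Z| < 1.96)
- Favourable direction: the same, with Z < 1.96 in place of |Z| < 1.96.

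**4. Results.**

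| n_B / N | √f | A and B | A, B and C | A and B, favourable | A, B and C, favourable |
|---|---|---|---|---|---|
| 18/90 | 0.447 | 9.2% | 11.2% | 4.6% | 5.7% |
| 24/90 | 0.516 | 9.0% | 11.3% | 4.5% | 5.7% |
| 18/99 | 0.426 | 9.3% | 11.1% | 4.6% | 5.6% |
| 24/99 | 0.492 | 9.1% | 11.3% | 4.6% | 5.7% |

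Independent tests would give 1 − 0.95² = 9.75% for two and 1 − 0.95³ = 14.3% for three. The table is lower because A contains B and C. Adding the 0.0052 interim look, taken on 30 adults, and testing A at 0.0498 gives 9.3% to 9.6% for A and B, and 11.4% to 11.5% for all three.

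**5. Does the stated model fit the single cohorts?** The only age groups defined for analysis are those of Cohorts B and C. If the age-group covariate uses them, it is constant within B and within C and cannot be estimated there. The model as written works only in A.

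**6. After the change.** If B and C are descriptive, or are tested only after A succeeds, the error across cohorts at a single final look is that of A alone: 5.0% when A is tested at 0.05. If all three were kept in parallel, a common two-sided level of about 0.021 each would hold 5%.

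**The case against.** The strongest reply is that the protocol, read as a whole, intends one confirmatory test in Cohort A. Much of this stands:

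- The age-group covariate fits only A.
- The plural in 13.3.3 is weak evidence, since 13.3.2 also uses the plural loosely for the as-treated safety population.
- The ITT population is defined once, as everyone randomised who took at least one dose.
- A power statement is a sample-size justification and not an allocation of alpha.
- A single alpha plan is what one confirmatory test would need.

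A reader might infer that the protocol sets up three confirmatory tests and so carries a false-positive rate of 11%. The document does not support that. It states no level for Cohort C, and nowhere says that success in B or C alone makes the trial positive.

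It can also be said that testing order belongs in the SAP, which was not available here. That is fair as to the missing order, and its absence is not the point. The point is what the protocol does state: a full 0.05 for Cohort B, separate analyses that are mandatory in 13.1 and optional in the synopsis and Section 3, and a plural in 13.3.3 against a singular in the synopsis. An SAP naming A alone would have to choose between these passages. The deferral to the SAP in 13.3.3 follows the text on missing data and MMRM and does not mention multiplicity.

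**Conclusion.** The contradiction is real and should be resolved. The weight of the text favours Cohort A as the intended primary population, but Sections 13.1 and 13.3.3 leave room for another reading.

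The size is conditional. Only if a significant result in a single cohort may be claimed as success is the chance of at least one false positive about 9% (A and B, the cohorts with a stated 0.05) or about 11% (if C is also tested at 0.05, an assumption). In the favourable direction the figures are about 4.5% to 4.6% and 5.6% to 5.7%, against 2.5%. They rest on normal test statistics, equal variances and equal allocation ratios across cohorts.

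A reader might also infer that naming A, at the alpha given in 13.2, restores 5%. It does not, because the stated interim and final levels give about 5.3% for A on its own.

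**What to change.** - In Section 13.1, Section 13.3.3 and the synopsis, state that Cohort A (all randomised and treated subjects) is the only confirmatory test of the primary outcome.
- Report Cohorts B and C as supportive estimates with 95% confidence intervals and nominal p-values. Alternatively, test them in a stated fixed order, only after A succeeds.
- Use the same wording in 13.1, Section 3 and the synopsis on whether the separate analyses will or may be done.
- Present the Cohort B power statement as supportive and not as a separate confirmatory test.
- State that the age-group covariate applies to the combined analysis.
- Correct the final-analysis alpha for A separately, so that the interim and final levels together hold 0.05.

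The cost is a few sentences, with no change to conduct or sample size. The downside is that no stand-alone significance claim is available for adolescents or adults if Cohort A fails.

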### 13.2 Interim Data Analysis

When the first 30 treated subjects have completed the Week 12 visit, summary and individual safety data will be submitted to the DSMB for review to support expanding enrollment in TOL-3021 studies to adolescent subjects aged 12.0 to <18 years of age.

An interim analysis will be performed when the first 30 subjects complete 24 weeks of treatment. The DSMB will review data in a blinded manner. Alpha spending will be utilized by the O'Brien-Fleming method, with 0.0052 of the alpha being spent at the interim analysis, saving the remaining 0.0498 alpha for the final analysis. Criteria for the review and any decision will be agreed with the DSMB. A small group of Tolerion management who are not related to the conduct of the trial will be provided unblinded data results from this interim analysis for administrative purposes. This list of individuals to be unblinded will be identified, and the process for these individuals to receive unblinded data results will be finalized prior to the unblinding for this interim.

Unblinded data summaries including safety outcomes and efficacy assessments will be prepared for the sponsor during the study using all data collected through Week 36. A final analysis of the data will be conducted at 52 weeks.

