--	--

	
A Data Safety Monitoring Board (DSMB) was established prior to study initiation to review data throughout the study, including the Week 12 data review described below.
 
When the first 30 treated subjects completed the Week 12 visit, all available data was compiled and provided to the DSMB to consider if the enrollment of adolescent subjects (aged 12 - <18) in TOL-3021 studies can be recommended. Summary and individual subject data were provided for DSMB and FDA review. If no objection is received from regulators and IRBs, then sites will be notified that they may begin enrollment of subjects aged 12 - < 18.
 
In addition, an interim analysis will be performed when the first 30 subjects have completed 24 weeks of treatment to evaluate the treatment response. Alpha spending will be performed using an O'Brien-Fleming approach.
 
Subjects will be asked to continue in the study for a 2-year safety follow-up period after completion of the 52-week double-blind study. During this 2-year follow-up subjects will have clinic visits at 18, 24, and 36 months from their first dose in the blinded study to evaluate safety. At each of these follow-up visits, a MMTT will be administered.

Study Outcomes
	
Primary Efficacy Outcome                  The primary outcome is the TOL-3021 treatment effect as determined by a repeated measures analysis of change from baseline in the log-transformed MMTT C-peptide AUC at 12, 16, and 24 weeks.
 
Secondary Efficacy Outcomes                  Secondary outcomes will include the treatment effect on:
 
 
• Rates of clinically important hypoglycemia events as defined by total measured glucose value of <54 mg/dL (3.0 mM/L) over each approximately 12-week period ending at Weeks 12, 24, 36, and 52:                         
 
○ A single blood glucose level.
 
○ By CGM, ≥10 consecutive minutes with glucose <54 mg/dL
 
 
 
• Total daily insulin requirements in units per kilogram (kg) body weight.
 
• HbA1c.
 
• Time in glycemic range 70 - 180 mg/dL
 
 
Other Secondary Endpoints  The TOL-3021 treatment effect—
 
 
• On a repeated measures analysis of change from baseline in the log-transformed MMTT C-peptide AUC at 12, 16, 24, and 52 weeks.
 

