### **13.3 Data Analysis**

Primary endpoint analyses will be conducted after all enrolled participants have completed Week 24. A final analysis of all data will be conducted after Week 52 is complete. Safety data and efficacy analyses will be updated at Week 36.

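### Section 13.2's interim and final alpha levels (0.0052 and 0.0498) add to 0.055, do not match O'Brien-Fleming at 30 of 90 subjects, and give about 0.053 overall

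*Protocol*

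**What the plan says.** Section 13.2 of the protocol names the O'Brien-Fleming method and splits the alpha "with 0.0052 of the alpha being spent at the interim analysis, saving the remaining 0.0498 alpha for the final analysis". The synopsis (Study Procedures) also names O'Brien-Fleming, without levels, and gives the timing and purpose of the look: "an interim analysis will be performed when the first 30 subjects have completed 24 weeks of treatment to evaluate the treatment response".

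The overall level comes from section 13.1: "A total of 90 subjects will provide 90% power to detect this difference at a significance level (alpha) of 0.05". That section allows up to 99 randomized subjects to cover dropout. Section 13.3.3 tests the null hypothesis "versus the two-sided alternative".

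On the later analyses, section 13.2 states that "A final analysis of the data will be conducted at 52 weeks", and section 13.3 states that "Primary endpoint analyses will be conducted after all enrolled participants have completed Week 24".

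**The concern.** Three things are wrong with the split.

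- **Arithmetic.** Section 13.2 describes 0.0498 as what is left after 0.0052 has been spent. With a total of 0.05 it is not.
- **Method.** The two levels are not a pair that O'Brien-Fleming produces for a look at about one third of the information. The interim level is much too large.
- **Target.** The 0.0498 is reserved for the final analysis, a term the same section uses for Week 52. The primary test is at Week 24, so read literally the primary test has no assigned level.

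At stake is the 5% two-sided error claimed for the primary test. An early efficacy claim could also rest on about 20 active and 10 placebo subjects (2:1 of 30) at p just under 0.0052, which is not the stringent early hurdle that the named method implies.

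**Working it through.** **Inputs**

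- Overall alpha 0.05 (section 13.1), two-sided (section 13.3.3).
- Interim 0.0052, final 0.0498 (section 13.2).
- Interim at the first 30 subjects with 24 weeks (synopsis, section 13.2); 90 evaluable, up to 99 randomized (section 13.1).
- Assumption: information is proportional to the number of subjects with Week 24 data. The information fraction is then t = 30/90 = 0.333 or 30/99 = 0.303.

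**Step 1: the stated split as amounts of alpha**

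0.0052 + 0.0498 = 0.0550, not 0.05. The remainder after spending 0.0052 is 0.05 − 0.0052 = 0.0448.

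**Step 2: the stated split as nominal two-sided thresholds**

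The critical values are z = 2.794 for 0.0052 and z = 1.962 for 0.0498. Under the null, the interim and final statistics are bivariate normal with correlation √t. The overall error is P(|Z1| > 2.794 or |Z2| > 1.962).

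| t | √t | Overall error, integration | Simulation (4 million draws) |
|---|---|---|---|
| 30/99 | 0.550 | 0.0530 | 0.0531 |
| 30/90 | 0.577 | 0.0528 | 0.0529 |
| 0.5 | 0.707 | 0.0518 | 0.0519 |

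The pair comes within 0.05 only for a very late look (0.0503 at t = 0.75, 0.0498 at t = 0.90).

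**Step 3: what O'Brien-Fleming gives**

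The classical two-look rule uses a final critical value c and an interim value c/√t, with c solved so that the overall error is 0.05.

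| t | Final c | Interim c/√t | Interim level | Final level |
|---|---|---|---|---|
| 30/99 | 1.961 | 3.563 | 0.0004 | 0.0498 |
| 30/90 | 1.962 | 3.399 | 0.0007 | 0.0497 |
| 0.5 | 1.977 | 2.797 | 0.0052 | 0.0480 |

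Lan-DeMets O'Brien-Fleming-type spending at t = 1/3 depends on the convention:

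- Applied directly to two-sided 0.05: 2[1 − Φ(1.960/√(1/3))] = 2[1 − Φ(3.395)] = 0.0007, with a final level of 0.0497.
- Applied to 0.025 per side and doubled: 0.0002, with a final level of 0.0499.

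So 0.0052 matches a half-way look and 0.0498 matches a look at about 0.30. Neither rule produces both together. At 30/90 the stated interim level is 0.0052/0.00068, about 8 times the classical level. Against the per-side convention it is 0.0052/0.00021, about 25 times.

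**Step 4: what would be coherent if 0.0052 were kept**

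Solving for the final level that returns an overall 0.05 gives 0.0469 at 30/90 and 0.0467 at 30/99. The literal remainder, 0.0448, is conservative: overall error is 0.0480 at 30/90 and 0.0481 at 30/99.

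**Step 5: power at the final look**

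Start from the stated 90% at 0.05 (1.960 + 1.282 = 3.242) and take power as Φ(3.242 − z) at each final level.

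| Final level | z | Power |
|---|---|---|
| 0.0497 | 1.963 | 90.0% |
| 0.0469 | 1.987 | 89.5% |
| 0.0448 | 2.007 | 89.2% |

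**The case against.** The strongest reply is that the excess is conditional and small. Section 13.2 states no efficacy stopping rule: decision criteria are still to be agreed with the DSMB, and a small group in sponsor management sees results for administrative purposes. If nothing can be rejected at the interim, a later test at 0.0498 keeps the error below 0.05. That is right as far as it goes. But the protocol expressly spends alpha at this look, and the synopsis gives its purpose as evaluating treatment response. An efficacy claim is therefore not ruled out, and alpha spent at a look that cannot reject has no function.

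A second reply is that 0.0498 is a slip, perhaps for 0.0448 or 0.0480. Nothing in the protocol shows how either figure was derived, so the match to two different information fractions is an inference about origin. A slip for 0.0448 would keep the error within 0.05, although the interim level would still not be O'Brien-Fleming at one third. A slip for 0.0480 would not cure the problem: 0.0052/0.0480 gives 0.0511 at 30/90 and 0.0513 at 30/99.

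Third, the information fraction could exceed one third if the interim model also uses Week 12 and Week 16 data from later enrollees. That changes the size, not the direction, since the excess persists at t = 0.5.

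Finally, section 13.3 does place the primary analysis at Week 24, so the Week 52 ambiguity is a matter of wording, separate from the arithmetic.

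**Conclusion.** The point stands, and it must be corrected. As written, the split allocates 0.055. As nominal thresholds, it gives an overall two-sided error of about 0.053 at the planned timing (0.0528 at 30/90, 0.0530 at 30/99). It also contradicts the named method: the interim level is about 8 times the O'Brien-Fleming value at 30/90 under the classical rule or direct two-sided spending.

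The error figures assume that efficacy may be declared at the interim and that information is proportional to subjects with Week 24 data. The sum and the mismatch with O'Brien-Fleming do not need the first assumption. The inflation itself is modest, about 0.3 percentage points. The correction is required because the protocol fixes wrong decision thresholds for its primary test.

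**What to change.** Replace the split in section 13.2 with one coherent pair for a look at 30/90, and name the convention:

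- **Classical O'Brien-Fleming**, or Lan-DeMets spending applied directly to two-sided 0.05: interim 0.0007, final 0.0497.
- **Lan-DeMets O'Brien-Fleming-type spending at 0.025 per side**: interim 0.0002, final 0.0499.
- **If 0.0052 is wanted at the interim**: final 0.0469 (0.0467 at 30/99), without the O'Brien-Fleming label. The simple remainder of 0.0448 is also valid but conservative.

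State that these are nominal two-sided levels, that the final level applies to the Week 24 primary analysis and not to Week 52, and that it is recomputed from the information fraction actually reached at the interim. Drop the description of the final level as the remainder unless 0.0448 is chosen. State whether efficacy may be declared at the interim.

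The cost is a sentence or two and no extra subjects. Final-look power stays at 90.0% with 0.0497, and falls to 89.5% with 0.0469 or 89.2% with 0.0448. The change has to be made before interim results are unblinded, because boundaries altered afterwards would not be credible.

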When the first 30 treated subjects completed the Week 12 visit, all available data was compiled and provided to the DSMB to consider if the enrollment of adolescent subjects in TOL-3021 studies can be recommended. Summary and individual subject data were provided for DSMB and FDA review. The DSMB confirmed that the protocol can be amended to include subjects aged 12 - < 18 years of age and submitted to FDA. If no objection is received from regulators and IRBs, sites will be notified that they may begin enrollment of subjects aged 12 - <18.

Subjects and investigators will be blinded to treatment assignment throughout the study. Selected Emmes staff will have access to treatment assignments. The primary data analysis will be conducted on data collected through Week 24. Cohorts B and C may be analyzed

separately. An interim analysis will be completed after the first 30 patients have completed 24 weeks. Results of the interim analysis will be shared with the DSMB and with a limited number of Tolerion staff, not directly involved in running the trial. Unblinded data summaries including safety outcomes and efficacy assessments will be prepared for the sponsor during the study using all data collected through Week 36. Final analysis of the data will be conducted at 52 weeks. The data summaries are unblinded to Sponsor and Emmes, the CRO, only.

Subjects will continue in the study for a 2-year safety follow-up period after completion of the 52-week double-blind study. During this 2-year follow-up subjects will have clinic visits at 18, 24, and 36 months from their first dose in the double-blind study to evaluate safety. At each of these follow-up visits a MMTT will be administered. Subjects may also be offered the opportunity to continue on study medication in a follow-on protocol for one or more years. Any follow-on study will continue to monitor subject safety in line with the requirements of the SUNRISE protocol.

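### The alpha kept back at the interim is assigned to an analysis that the protocol dates at Week 52, while the primary test is at Week 24

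*Protocol*

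**What the plan says.** **The alpha rule (Section 13.2).** The interim takes place at Week 24 of the first 30 subjects: "An interim analysis will be performed when the first 30 subjects complete 24 weeks of treatment". The rule is: "Alpha spending will be utilized by the O'Brien-Fleming method, with 0.0052 of the alpha being spent at the interim analysis", followed by "saving the remaining 0.0498 alpha for the final analysis".

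**What the protocol calls final.** The last paragraph of Section 13.2 says "A final analysis of the data will be conducted at 52 weeks". Section 3 says "Final analysis of the data will be conducted at 52 weeks". Section 13.3 also puts a final analysis of all data after Week 52.

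**What the protocol calls primary.** Section 13.3 says "Primary endpoint analyses will be conducted after all enrolled participants have completed Week 24". Section 3 and the synopsis (Data Handling and Blinding) place the primary analysis at Week 24 as well. Section 4.3 limits the primary outcome to C-peptide AUC at Weeks 12, 16 and 24. The same analysis extended to Week 52 is listed under other secondary outcomes (Section 4.5 and synopsis).

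**The level in the power statement (Section 13.1).** For the Week 12, 16 and 24 endpoint: "A total of 90 subjects will provide 90% power to detect this difference at a significance level (alpha) of 0.05". The statement does not mention the interim look.

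**The concern.** A group-sequential rule has to name the analysis that receives the alpha left after the interim. Here the recipient is named by a term that the protocol, wherever it dates an analysis of the data, attaches to Week 52. Taken at its word, the plan holds back a level for a secondary time point and gives none to the test on which the trial's primary conclusion rests. An SAP that followed Section 13.2 faithfully would carry this forward.

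The ambiguity matters more because of the unblinding plan. The sponsor is group-unblinded after the Week 24 analysis (synopsis and Section 3) and receives unblinded efficacy summaries through Week 36 (Section 13.2). After an unsuccessful Week 24 result, Section 13.2 could be cited as having reserved a level for C-peptide at Week 52.

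**Working it through.** **Step 1. Set the terms side by side.**

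| Place | Week 24 analysis | Week 52 analysis |
|---|---|---|
| Synopsis, Data Handling and Blinding | primary | not named |
| Section 3 | primary | final |
| Section 13.2 | not named | final |
| Section 13.3 | primary | final |

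No section calls the Week 24 analysis final. Section 13.2 never uses the word primary, so nothing in that section points the saved alpha back to Week 24.

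**Step 2. Check the plan's own levels.** The primary test is two-sided ("versus the two-sided alternative using the intent-to-treat (ITT) cohorts", Section 13.3.3).

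- As shares of alpha: 0.0052 + 0.0498 = 0.0550, not 0.05. The additive remainder would be 0.05 − 0.0052 = 0.0448.
- As nominal levels at two looks on the Week 24 endpoint: the two test statistics have correlation √t, where t is the information fraction. The overall error is 1 − P(|Z1| < 2.794 and |Z2| < 1.962). With t = 30/90 = 1/3 (correlation 0.577) this is 0.0528. With t = 30/99 = 0.303 it is 0.0530.
- Solving for the second level that gives exactly 0.05 with 0.0052 kept: 0.0469 at t = 1/3 and 0.0467 at t = 0.303.

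So the stated pair does not reproduce 0.05. That is a separate error in the same sentence, and it means that 0.0498 cannot simply be moved to Week 24.

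**Step 3. Size of the ambiguity.** Suppose the three-visit primary analysis is tested at 0.05 (Section 13.1) and the listed four-visit analysis at 0.0498 (Section 13.2). The protocol gives no between-visit correlation. Assume one common value ρ and equal variances, and treat each analysis as the average over its visits. The correlation of the two test statistics is then

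r = √[ 3(1 + 3ρ) / (4(1 + 2ρ)) ].

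The chance of at least one false positive is 1 − P(|Z1| < 1.960 and |Z2| < 1.962) for a bivariate normal with correlation r.

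| ρ (assumed) | r | Chance of at least one false positive |
|---|---|---|
| 0.9 | 0.996 | 5.4% |
| 0.7 | 0.984 | 5.8% |
| 0.5 | 0.968 | 6.2% |

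These figures leave out the interim, so that the error in Step 2 is not counted here.

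**Step 4. Effect on power.** The protocol states no SD. Back-solve it from 90% power at two-sided 0.05, where the standardised effect is 1.960 + 1.282 = 3.242. Power at 0.0498 is Φ(3.242 − 1.962) = 89.97%. At 0.0469 it is Φ(3.242 − 1.987) = 89.5%. Sample size is not the issue.

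**The case against.** The best defence is that final, in the alpha sentence, is the ordinary counterpart of interim: the last look at the same hypothesis. The interim uses Week 24 data on 30 subjects, so its natural partner is Week 24 data on all subjects. That is probably what was meant. It makes the repair easy, but it does not make the text right, because the same section dates its final analysis at Week 52.

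Three stronger readings are tempting, and the documents do not support them.

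- **That the protocol defines the final analysis as Week 52.** It uses the term that way consistently but nowhere defines it. Section 12.5 also speaks of final analysis datasets in connection with the Month 36 lock.
- **That the trial plans two confirmatory tests.** The outcome hierarchy says otherwise: the primary outcome stops at Week 24, and C-peptide including Week 52 is an other secondary outcome. No section instructs anyone to test Week 24 at 0.05 and Week 52 at 0.0498. The 0.05 in Section 13.1 is a design assumption in a power statement.
- **That the error rate reaches 7% to 9%.** Figures of 6.7% to 8.7% arise only if Week 52 is tested as a single-visit MMTT AUC contrast, which the protocol does not list. Figures that add the interim also absorb the separate fault in the 0.0052 and 0.0498 pair, which alone gives about 5.3%.

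What stands is the textual point: the alpha rule names the wrong analysis, and the outcome hierarchy does not correct it because it says nothing about levels. Nor is this a detail left to the SAP. The protocol itself fixes the method, the two levels and the recipient.

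**Conclusion.** The concern holds as a misassignment in the wording of Section 13.2. As written, the remaining alpha goes to an analysis dated at Week 52, and the Week 24 primary endpoint keeps only the unadjusted 0.05 of the power statement. If both levels were used, the chance of at least one false positive would be about 5.4% to 6.2% instead of 5%, before the interim is counted. That range rests on an assumed between-visit correlation of 0.9 to 0.5 and on a testing scheme that the text permits but does not prescribe. The inflation is modest and the effect on power negligible. The weight of the point is that the protocol should leave no doubt about which test is confirmatory, especially as the sponsor sees the Week 24 result well before Week 52. It should be corrected.

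**What to change.** 1. In Section 13.2, replace the reference to the final analysis in the alpha sentence with *the primary analysis at Week 24 of all randomised subjects*.
2. In the same edit, recompute that level so that it and the interim level together give two-sided 0.05. If 0.0052 is kept at information 1/3, the Week 24 level is about 0.0469. Carrying 0.0498 over unchanged would leave the overall level at about 0.053.
3. Cite the resulting level in Section 13.1 in place of the unadjusted 0.05.
4. State that the Week 36 and Week 52 efficacy analyses are secondary and carry no alpha for the primary hypothesis.

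The cost is a few sentences in Sections 13.1 and 13.2 and one short calculation. With the SD back-solved from the stated 90% power, power at 0.0469 is still about 89.5%, so the sample size need not change.
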